Primary efficacy outcome analysis: Analysis by linear mixed models for repeated measures (LMM_R) of the within-group (TPTD) change in LS aBMD (g/cm²) by DXA from pre-treatment baseline with repeated measures at 12- and 24-months. (This is a growth curve model testing the hypothesis that the temporal trajectory of within-subject change in outcome differs from a random process.) The model estimates the fixed effect of time, random effects for subject, error and the quadratic and cubic values of time entered as random effects, continuous covariates for age and weight at baseline and with an AR(1) covariance structure. The random effects for higher-order factors for time model monotonic and U-shaped components of the growth curve. Model estimated within-subject differences between specific timepoints will be assessed when the fixed effect of time is statistically significant. The LMM_R model will be repeated for LS trabecular vBMD by cQCT after 24 months of teriparatide. Secondary efficacy outcome analysis: The same LMM_R analysis proposed for Aim 2 primary outcomes

will be used for secondary efficacy outcomes of TH, FN and $1/3^{rd}$ RD aBMD by DXA and HRpQCT after 12 and 24 months, and cQCT after 24 months of TPTD. These analyses will also be used to explore the pattern of change in serum BTMs (P1NP and CTx), between baseline and 24 months. Exploratory analyses will also be conducted to determine whether clinical factors such as age, BMI, body composition, and aspects of the growth hormone axis may predict BMD response to TPTD.

2.B. Power and Sample Size

We have based our power calculations upon the preliminary data generated from our recent pilot study of 22 women with IOP who were treated with teriparatide for 24 months. Our power estimates are based upon 40 women randomized to TPTD or placebo (28:12) with data for analysis, assuming a 10% drop-out and an alpha level of 5%.

AIM 1:

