Primary efficacy outcomes: For MdPm and BFR/BS after 3 months of TPTD, we base our effect size assumptions on the Lindsay et al²⁸ estimates of changes from baseline to 1-month of cyclic TPTD treatment (assuming these measures are virtually unchanged over 3 months in the placebo treated group). Lindsay reports cancellous BFR/BS increased from 0.008 ± 0.006 to 0.027 ± 0.018 (a standardized effect size of 1.42) and cancellous MdPm from 1.33 ± 0.95 to 3.78 ± 2.53 after 1 month (a standardized effect size of 1.28). With the proposed sample size, we will have over 90% power to detect difference comparable or larger than the increase in bone formation detected by Lindsay after 1-month of treatment. Secondary analyses to assess the predictability of DXA and cQCT changes from baseline and 3-month changes in BFR/BS and MdPm: The proposed sample size enables us to detect between 40% to 55% of the variance accounted for in the 12- or 24-month DXA or cQCT change and the baseline to 3-month change in BFR/BS or MdPm (assuming 80% power, 5% alpha and a multiple regression model with up to 3 covariates partialled from both the bone density outcome and the histomorphometric predictor).

AIM 3:

Primary efficacy outcomes: For LS aBMD by DXA after 12 and 24 months of TPTD, we will have >86% power to detect changes from baseline. We based our estimate of LS aBMD at 12 months on our preliminary data, and at 24 months on the data of Graeff et al.⁴¹ who detected a 10.2% increase in aBMD over 24 months. We anticipate that the increase between baseline and 12 months will far exceed the increase from 12 to 24 months, which may not be statistically significant. For trabecular vBMD at the spine by cQCT after 24 months of TPTD, the work of Rehman et al.³², who detected an increase of 35% in vBMD, suggests that we will have power of >99% to detect within-group changes.

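### The Aim 3 model puts curvature only in random effects and does not say how fixed time is coded; if time is one continuous term, equal first- and second-year gains are built in

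*Combined protocol and SAP*

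**What the plan says.** Section 2.A, Aim 3, primary efficacy outcome analysis, specifies a linear mixed model for lumbar spine aBMD "from pre-treatment baseline with repeated measures at 12- and 24-months". On its terms it says: "The model estimates the fixed effect of time, random effects for subject, error and the quadratic and cubic values of time entered as random effects". Age and weight are covariates, and the errors are modelled "with an AR(1) covariance structure". No fixed quadratic or cubic term is listed.

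The section then gives the purpose of the random terms: "The random effects for higher-order factors for time model monotonic and U-shaped components of the growth curve". It describes the whole as follows: "This is a growth curve model testing the hypothesis that the temporal trajectory of within-subject change in outcome differs from a random process". Follow-up comparisons are gated: "Model estimated within-subject differences between specific timepoints will be assessed when the fixed effect of time is statistically significant". Whether fixed time is continuous or categorical is not stated.

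The same model is carried to total hip, femoral neck and 1/3 radius aBMD, HR-pQCT, cQCT and, for exploration, the turnover markers.

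Section 2.B, Aim 3, states the expected shape: "We anticipate that the increase between baseline and 12 months will far exceed the increase from 12 to 24 months". It adds that the second-year increase may not reach significance. For total hip it claims 99% power against baseline at 12 and 24 months, but possibly too little power between 12 and 24 months.

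**The concern.** A random quadratic or cubic coefficient is a deviation around a population mean of zero. It lets individual curves differ in curvature but adds nothing to the average curve. The SAP's statement about what these terms do is therefore wrong for the population mean, however time is coded.

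The practical consequence depends on that coding. Growth-curve language and powers of time point to a continuous term. With a single continuous term, the average can only be a straight line, so the model cannot return the decelerating pattern that section 2.B predicts. Aim 3 asks how much BMD improves at 12 months as well as at 24. On this reading the 12-month estimate is biased downward when gains slow, and a second-year plateau would be reported as continued gain. Two analysts following the same paragraph could reach opposite conclusions about the second year.

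**Working it through.** **The plan's own figure.** Section 2.B gives power above 86% for change from baseline. It cannot be reproduced or refuted, because neither the 12-month mean nor the SDs of change at 12 and 24 months are given. For a two-sided paired test at 5%, 86% power needs a standardized change of 0.49 (n = 40), 0.52 (n = 36) or 0.60 (n = 28). The point below does not depend on this figure.

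**Algebra, continuous time.** Take t in years, with baseline, 12 and 24 months as three occasions. For one woman, leaving covariates aside:

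Y(t) = β0 + β1·t + b0 + b2·t² + b3·t³ + e(t), where b0, b2, b3 and e have mean zero.

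- Mean gain 0-12 months: β1
- Mean gain 12-24 months: β1
- Mean gain 0-24 months: 2β1

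The test statistics are β1/SE, β1/SE and 2β1/(2·SE). They are identical to each other and to the gate test of time. Once the gate opens, all three contrasts are significant. This needs no assumption about variances.

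**Size of the bias.** The least-squares slope through three equally spaced means is (m24 − m0)/2. If the true yearly gains are g1 and g2, the fitted yearly gain is (g1 + g2)/2. The 12-month gain is then understated, and the second-year gain overstated, by (g1 − g2)/2. For the 24-month total I use the study that section 2.B cites, "who detected a 10.2% increase in aBMD over 24 months". The 12-month gain is not given, so I show a range:

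- g1 = 7.0 (low end of the annual range in section 2.B, Aim 1), g2 = 3.2: fitted 5.1 and 5.1; bias (7.0 − 3.2)/2 = 1.9 points.
- g1 = 8.0, g2 = 2.2: bias (8.0 − 2.2)/2 = 2.9 points.
- g1 = 10.2, g2 = 0 (full plateau): bias 10.2/2 = 5.1 points.

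**Simulation with the stated random terms and AR(1) errors.** Maximum likelihood, n = 36, 25 replicates per row. Assumptions, in % of baseline: between-woman SD 10, residual SD 2, random t² SD 0.5.

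| True mean at 0 / 12 / 24 months | Continuous time: gain in each year | Categorical time: 0-12 | Categorical time: 12-24 |
|---|---|---|---|
| 0 / 8 / 10.2 | 5.2 | 8.0 | 2.1 |
| 0 / 8 / 8 | 4.2 | 7.9 | 0.1 |
| 0 / 8 / 6 | 3.1 | 7.9 | −2.2 |
| 0 / 5.1 / 10.2 | 5.1 | 5.0 | 5.2 |

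Continuous time was significant in every replicate. Residual SD 3.3 (the SD that section 2.B gives for 6-month change on TPTD) left the plateau row at 4.2 per year. Averaging the women's own predicted curves, random terms included, gave 4.2 then 3.9 in the plateau row, so the random effects do not rescue the mean.

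A separate REML simulation assumed 37 women, baseline SD 10%, response CV 0.45 and scan error SD 1.2%, with 150 runs per case. With true gains of 7.0 and 3.2, continuous time gave 5.1 (SE 0.4) for each year. The 95% intervals covered the true yearly gains in at most about 1% of runs, while coverage for the 0-24 month change was 91-96%.

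**The case against.** A reader might infer that the plan commits to a straight line and will report a plateau as continued gain. The documents do not support that. The SAP nowhere says fixed time is linear, and several features fit categorical time. Timepoint differences assessed after a significant time effect is the usual sequence of an omnibus test and then contrasts; with one slope, that second step would be empty. Section 2.B treats the 12-24 month comparison as having its own, lower power for both spine and total hip, which is possible only if the contrasts can differ. Under categorical time the simulation recovers the true gains, plateau included. Also, if the outcome is change from baseline at 12 and 24 months only, a free intercept and a slope fit both means exactly, and equal gains are not forced.

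The consequence is limited too. Aim 3 concerns change from baseline rather than the added value of year two, and the protocol lists it as secondary. The spine cQCT outcome has one follow-up scan, so a line through two occasions fits its mean exactly.

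All of this stands, and it makes the numerical consequence conditional. It does not rescue the statement that the random effects model the curve's shape. Nor does it settle the coding: categorical time at three occasions would already leave the mean free, so the stated reason for the higher-order terms makes sense only beside a linear fixed term.

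**Conclusion.** The concern holds in conditional form. The sentence that assigns the curve's shape to the random effects is wrong for the average woman under any coding. The coding of fixed time is unstated, and the text points both ways. If it is one continuous term with baseline among the occasions, equal yearly gains and a shared p-value follow by algebra, contrary to section 2.B. The 12-month gain is then understated by about 1.9 to 5.1 percentage points over the range shown. If time is categorical, none of this occurs.

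The equal-gains result needs no variance assumptions. The size of the bias rests on the assumed 12-month gain, and the coverage figures also rest on assumed SDs. The 0-24 month change is about right on either coding, and cQCT is unaffected. This should be fixed before analysis, because choosing the coding after seeing the data would be a post hoc choice about the second-year result. It does not invalidate the aim.

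**What to change.** In section 2.A, Aim 3, primary efficacy outcome analysis:

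- State that time on TPTD enters as a categorical fixed factor (0, 12 and 24 months). If a curve is preferred, add a fixed quadratic term; at three occasions the two give the same mean.
- Define the 0-12, 0-24 and 12-24 month changes as contrasts of the fitted means.
- Replace the sentence on the higher-order random effects with one saying that they describe variation between women around the mean curve.
- Apply the same mean structure to the secondary DXA, HR-pQCT and turnover-marker models.

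Adding the 6- and 18-month DXA scans, which the design already schedules, and dropping the quadratic and cubic random effects are both optional. Neither is needed to correct the mean.

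The cost is a paragraph of SAP wording and one extra fixed-effect degree of freedom with three occasions (2 rather than 1), or three with five occasions (4 rather than 1). No new data are needed.

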randomized, double blind, placebo-controlled, single switch-over trial of TPTD in premenopausal women with IOP. Forty-one subjects will be assigned to TPTD (Group A; n=28) or placebo (Group B; n=13). At the 6 month timepoint, all subjects will receive TPTD, but blinding of original group assignment will be maintained for an additional 6 months. At the 12 month visit, the blind will be broken and those initially randomized to TPTD (Group A) will continue on study drug for an additional 12 months while those initially randomized to placebo (Group B) will continue for an additional 18 months, so that subjects in both groups complete 24 months of treatment overall. aBMD by DXA and HRpQCT will be measured at baseline and at 6 month intervals. vBMD by cQCT will be performed before randomization and after 24 months of TPTD (Table 1). A quadruple labeled transiliac crest bone biopsy will be performed at 3 months for both Group A and B. Eli Lilly & Company will provide TPTD and placebo but will supply no other funding. After 24 months of treatment in either Group A or B, all women will be offered three choices for follow up: the subjects can A) continue to to be followed for 12 months off TPTD B) choice to leave the study and be treated clinically using an anti-resorptive medication to maintain gains in bone density after treatment with TPTD, or C) join a new study to maintain gains in bone density after treatment. The new study is currently in the design phase and funding phase and precise details are not yet available.

Statistical Analysis Plan

2.A. Statistical Analysis Plan Our aims in this protocol are as follows:

Aim 1: To establish the efficacy and safety of 6 months of TPTD versus placebo in premenopausal women with IOP

Aim 2: To determine the effect of 3 months of TPTD on bone remodeling at the tissue level and the extent to which baseline and 3 month bone remodeling predicts response to TPTD in premenopausal women with IOP.

Aim 3: To determine the extent to which 12 and 24 months of TPTD improves areal and volumetric BMD, bone microarchitecture and strength (stiffness) compared to baseline measures in premenopausal women with IOP

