Subjects will be provided with calcium (citrate) caplets (Citracal + D; each 315 mg + 250 IU D) and a multivitamin (Centrum) that provides 500 IU of vitamin D daily. Most subjects will be instructed to take 2 Citracal caplets and a multivitamin; the total daily dose of calcium from supplements will be approximately 630 mg and of vitamin D 1000 IU. Subjects with very low dietary calcium intake (<500 mg/d estimated by interview and the FFQ), will be asked to take 3 Citracal caplets, while those with high dietary calcium intakes (>1,000 mg/day) will be asked to take 1 Citracal caplet.

Visits 4-5, 8-13 (Study Evaluations): At each study visit, study coordinators will assess any adverse events that transpired since the last study visit. Patients will be instructed to bring their Forteo journal and pens with them to every visit, which documents their compliance with the study medication. The purpose

of the 1-week and 1-month visits (Visits 4 & 5) is to monitor for compliance and adverse effects. At the 1-week and 1-month visit, we will also obtain fasting serum for serum calcium (safety) and at the 1-Month we will also collect serum for BTMs. These visits may be conducted on site for women who reside close to the study sites or may be a telephone contact and local blood draw for those who live at a distance. The remainder of the study visits to perform imaging studies and/or blood draws and dispense study drug are shown in Tables 1-3. We will perform a single follow-up cQCT scan after 24 months of TPTD treatment to minimize radiation exposure in these women who are of child-bearing age. At Visit 12, subjects will be presented with three options for post-TPTD follow up as described in the study design.

Visit 6 (Pre-Biopsy Clearance and Labeling): Subjects will have a pre-biopsy clearance visit with the surgeon and have safety bloods drawn and processed as per hospital regulations. Subjects will receive their second antibiotic labeling agent, demeclocycline, and accompanying labeling schedule.

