MD Visit		X	V	X	X				
Dispense TPTD		X	X X	X					
Telephone Contact [#]	X	X	X X	X	X				
Pregnancy Test BMD by DXA		X	X X	X	X				
History & Physical		X	Λ	X	X				
Adverse Events	v	X	Х	X	X				
Serum FSH	X	X	Λ	X	X				
HR-pQCT		x		X	X				
Central QCT		Λ		X X	Λ				
VFA by DXA		x		X	x				
		X	X	X	X				
Calciotropic Hormones		X		X	X				
Bone Turnover Markers		X	Х	X	X				
* Only for treatment									
treatment (Group A # Will occur before		luled visi	t						

Table 3: Study Visits – Group B**	9 9M	9 12M	10 18	11 24	12 30	13 42
Group D	>	12111	M	M	M	M
MD Visit		х		Х		Х
Dispense TPTD		Х	Х	Х		
Telephone Contact [#]	Х	X	Х	Х	Х	Х
Pregnancy Test		х	х	х	Х	Х
BMD by DXA		х	Х	Х	Х	Х
History & Physical		х		Х		Х
Adverse Events	х	х	Х	Х	Х	Х
Serum FSH					Х	
HR-pQCT			х		Х	Х
Central QCT					Х	
VFA by DXA		х		х		Х
Blood/Serum Archive	х	х	х	х	Х	Х
Calciotropic Hormones		х		Х		Х
Bone Turnover		х	Х	Х	Х	Х
Markers						
** Only for treatment group that started with 6 months of						
placebo injections (Group B)						

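### Group B has no bone turnover marker scheduled between 0 and 6 months on teriparatide, although its serum is already archived at 3 months on drug (study 9M)

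*Combined protocol and SAP*

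**What the plan says.** Section 2 sets the groups and the switch: "Forty-one subjects will be assigned to TPTD (Group A; n=28) or placebo (Group B; n=13"), then "At the 6 month timepoint, all subjects will receive TPTD", "so that subjects in both groups complete 24 months of treatment overall". Group B thus takes teriparatide from study month 6 to study month 30.

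In Section 2.A, Aim 3, the main model concerns "within-group (TPTD) change in LS aBMD (g/cm²) by DXA from pre-treatment baseline with repeated measures at 12- and 24-months". The turnover markers are added at the end of the secondary analyses: "These analyses will also be used to explore the pattern of change in serum BTMs (P1NP and CTx), between baseline and 24 months". No hypothesis, power or precision is stated for them.

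Table 1, common to both groups, marks turnover markers at randomization, 1M, 3M and 6M. The text of Section 3.A agrees for the first of the on-treatment draws: "at the 1-Month we will also collect serum for BTMs". In "Table 3: Study Visits – Group B", the row that begins "Bone Turnover" is blank at 9M and marked at 12M, 18M, 24M, 30M and 42M. The Blood/Serum Archive row of the same table is marked at 9M and at every later visit. Section 3.B, item 8, lists P1NP and CTx among the analytes whose serum is frozen at -80°, and provides in general terms for archived serum to be used for markers later. No text schedules a marker assay at 9M.

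**The concern.** Aim 3 describes how the markers move over 24 months of teriparatide. The shape of such a curve in its first months depends on the early samples. Group A has two inside the first half-year on drug (months 1 and 3). Group B has none, because the early draws in Table 1 fall in its placebo period and were not repeated after the switch.

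Three months on drug is also a time the protocol treats as important: Aim 2 concerns the effect of 3 months of teriparatide on remodeling. Group B's biopsy at study month 3 is a placebo biopsy. Its 9M serum is therefore the only scheduled sample that could show its turnover at 3 months on drug, and the serum will already be in the freezer. At stake is some precision, and the contribution of 13 of 41 women, at one point of an exploratory curve.

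**Working it through.** The plan gives no precision figure for the marker analysis, so there is none to reproduce.

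**Inputs.** Group sizes 28 and 13, and Group B's start of teriparatide at study month 6 (Section 2). Marker visits from Tables 1, 2 and 3. Drop-out of 10% (Section 2.B), for sensitivity only.

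**Step 1: put the visits on time since starting teriparatide.** For Group A this is the study month; for Group B it is the study month minus 6.

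- Group A: 0, 1, 3, 6, 12, 18, 24.
- Group B: study 6M, 12M, 18M, 24M and 30M become 0, 6, 12, 18, 24.

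**Step 2: count women with a scheduled marker.**

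| Months on drug | Group A | Group B | Total |
|---|---|---|---|
| 0 | 28 | 13 | 41 |
| 1 | 28 | 0 | 28 |
| 3 | 28 | 0 (13 if 9M is assayed) | 28 (41) |
| 6, 12, 18, 24 | 28 | 13 | 41 |

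The share observed at month 3 is 28/41 = 68%. With 10% drop-out the counts are 28 × 0.9 = 25.2 and 41 × 0.9 = 36.9.

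**Step 3: gain for a simple mean.** With equal variance, the standard errors are in the ratio √(28/41) = 0.83, a fall of 17%. The 95% half-width goes from 1.96/√28 = 0.37 SD to 1.96/√41 = 0.31 SD.

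**Step 4: gain in a mixed model.** Group B already contributes at months 0 and 6, so the simple-mean figure does not carry over. Take time as categories and pool both groups on time since starting drug. The information matrix is Σ n_g X_g′V_g⁻¹X_g, where X_g selects the months observed in group g and V_g is the covariance of those months. Invert it and read off the standard error of (month 3 − month 0), with and without Group B at month 3. The documents give no marker correlations, so ρ is assumed, either equal between all visits (compound symmetry) or decaying as ρ^(months apart/6). Standard errors are in units of one SD.

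| ρ | Structure | SE now | SE with 9M | Reduction |
|---|---|---|---|---|
| 0.1 | equal | 0.234 | 0.210 | 10.5% |
| 0.1 | decaying | 0.206 | 0.183 | 11.5% |
| 0.5 | equal | 0.176 | 0.156 | 11.3% |
| 0.5 | decaying | 0.134 | 0.120 | 11.1% |
| 0.9 | equal | 0.079 | 0.070 | 11.5% |
| 0.9 | decaying | 0.056 | 0.050 | 10.1% |

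The reduction is about 10-12% throughout. Equal drop-out in both groups scales both standard errors alike and leaves it unchanged.

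**The case against.** The strongest reply is that no stated analysis is impaired. The marker work is exploratory, the Aim 3 model names 12 and 24 months as its time points, and nothing in the SAP is powered or tested at 3 months on drug. Group B's five on-drug samples cover the whole 0-to-24-month span. The 9M serum is stored, so the assay could be run later without a protocol change. All of this stands, and it is why the point is minor.

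Three stronger readings are tempting, and the documents do not support them.

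- A reader might infer that Group B has no marker data for its first 6 months on drug, so that the early curve rests on Group A alone. Group B supplies both ends of that interval (study 6M and 12M). Only the observed values at months 1 and 3 are Group A's alone, and a fitted curve also draws on Group B at months 0 and 6.
- A reader might take 17% as the gain in precision. That compares two simple means and does not describe the planned type of analysis.
- A reader might say that a within-woman comparison of 3 months on placebo (3M) with 3 months on teriparatide (9M) is lost. The plan never proposes one. It would be a fixed-order, before-and-after contrast, whereas the draws at 1M, 3M and 6M already give a concurrent randomized comparison.

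The objection that the plan could always assay the serum later stands only in part. An unscheduled assay is a choice left open, and it may not be run in the same batch as the other samples.

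**Conclusion.** The point holds as an inexpensive improvement to an exploratory analysis. Observed P1NP and CTx at 3 months on drug will come from 28 of 41 women, although serum from the other 13 is due to be stored at exactly that time. Assaying it would reduce the standard error of the 0-to-3-month change by about 10-12%. It would not fill month 1, because Group B has no visit at study month 7.

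The figure rests on assumptions: that Aim 3 pools both groups by time on drug, that 6M is Group B's pre-treatment value, that variances and drop-out are equal in the two groups, and that correlations lie between 0.1 and 0.9. It was computed with time as categories, which simplifies the SAP's growth-curve model. The SAP does not say explicitly how Group B enters Aim 3 or which value is its baseline. The pooling assumption fits Table 3, which places HR-pQCT at 18M and 30M and central QCT at 30M, that is, at 12 and 24 months on drug. Nothing here affects the primary efficacy or safety analyses.

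**What to change.** In Table 3, mark P1NP and CTx at 9M for Group B and assay the stored 9M serum in the same batch as the other samples. In Section 2.A, Aim 3, state that the marker model places Group B on time since starting teriparatide, with its 6M value as the pre-treatment baseline and 9M as month 3.

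The cost is two assays on up to 13 stored samples, one mark in Table 3 and a sentence in the SAP. Group B needs no extra visit or draw.

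As a separate check, confirm that the 9M blood draw is the same in both groups. Assignment stays blinded to 12M. In the available text of Table 2 (Group A), one row has no label and appears blank at 9M; if it is the serum archive row, the two schedules differ during the blinded period. The text does not settle this, and the assay fix does not depend on it. If Group A has no 9M draw, making the schedules alike would add draws in up to 28 women, a cost not included above.
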